## **POTENTIAL BENEFITS**

Patients will be informed that there may be no direct benefit from participating in this research study. Some patients in the intervention condition of Phase III (*Active Brains-Fitbit*) may become more physically active, more resilient, better able to cope with pain and stress, and experience a better quality of life.

In the future, knowledge from this research may benefit others by providing information on how to better mind body interventions for patients with chronic pain and mild cognitive impairment **or** memory-related problems.

## **VIII. MONITORING AND QUALITY ASSURANCE**

#### Phase I:

The focus groups will be conducted uniformly using a semi structured interview script that will be finalized during the first few months of the study. The Principal Investigator will be responsible for ensuring compliance with IRB procedures.

#### Phase II/Phase III:

Electronic information will be stored in REDCap (Research Electronic Data Capture), a free, secure, and HIPAA-compliant web-based application hosted by the Partners HealthCare Research Computing Enterprise Research Infrastructure & Services (ERIS) group (based at the PHS Needham corporate datacenter). Data will be stored on password protected computers that will be stored in secure locations at all times. If any paper data files are used (with coded subject identification) will be stored in a locked filing cabinet. Only research staff will have access to these data locations.

A unique anonymous identifier will be assigned to each subject; subsequently, all data collected will be associated exclusively with this identifier. This includes all questionnaires administered over the course of the study, as well as home practice logs. Data from this study will be stored for three years after the publication of all study results, at which time all paper data files will be shredded and computer files will be deleted.

The group sessions will be conducted using a structured patient manual. The exit interviews will be conducted using a semi-structured interview script in Phase II and will use an unstructured exit interview format to solicit diverse feedback in Phase III. Once completed, a member of study staff will verify that all items on all questionnaires have been addressed. Data will be checked for out of range values using frequency distributions prior to analyzing the data. The PI will be responsible for ensuring compliance with IRB procedures.

Study Title: Managing Pain and Cognitions in Older Adults With Mild Cognitive Impairment or
Memory Related Problems and Chronic Pain

NCT04044183

Document Date: June 1, 2018

STATISTICAL DESIGN AND POWER

The present proposal aims to adapt, pilot and examine the credibility, acceptability, adherence and feasibility of the p3RP and the p3RP-DMD adapted for patients with MCI (Active Brains and Active Brains with Fitbit). We have already developed the p3RP and p3RP-DMD which are adapted for the specific needs of patients with chronic pain, but not MCI. The proposed R34 supplement feasibility project will lay the groundwork for a large RCT of the Active Brains vs Active Brains with Fitbit vs attention placebo control, and will help understand whether the DMD Fitbit is feasible and necessary to comprehensively improve function. Consistent with prior theory within a subsequent efficacy trial¹ we will test the hypothesis that the Active Brains with Fitbit will be superior to the Active Brains and HEP in improving and sustaining improvements in objective, performance based and self-reported physical and emotional function in patients with heterogeneous chronic pain comorbid with MCI. Using the supplement to the R34 mechanism we will follow an iterative design^{82,83} to adapt and refine both the p3RP and the integrated p3RP-DMD interventions to maximize feasibility, acceptability, credibility, recruitment protocol, adherence and measurements for patients with heterogeneous chronic pain. To allow objective measurement of activity in both Active Brains and Active Brains with Fitbit groups, we will use Accelerometer DMDs for 1 week at baseline and post-test. The Fitbit DMD will be used to address/reinforce activity consistent with an individualized pacing plan, and to assess daily activity during the program only for those randomized to the Active Brains. All procedures have already been piloted within our R34 and will easily be adapted for the supplement.

Power analyses:

This trial (Aim 2) is primarily focused on feasibility and acceptability, not statistical significance of efficacy. With a sample size of N=60 participants the study will have 80% power to confirm feasibility of each delivery modality if the true completion rate among eligible patients is at least 77%, much lower than the 100% retention we achieved in our preliminary studies^{15,16} of the 3RP in a different population.

Analyses plan:

Aim 1. We will report feasibility as number of screened, eligible participants, and enrolled participants, and number of participants who completed at least 6 out of the 8 sessions. We will also report information on preliminary acceptability from quantitative and qualitative data, as well as information on credibility of intervention and adherence to DMD and Active Brains homework. We will also calculate descriptive statistics for quantitative measures. Qualitative Data Analyses: The qualitative focus group data and individual exit interview data will be transcribed and analyzed, using NVivo 10 qualitative software, and we will conduct thematic content analysis using guidelines provided by Miles and Huberman (1984)⁹⁹. The 2 coders (study clinician and research assistant) will meet on an ongoing basis with [name] to discuss the structural thematic framework, categories, and coding plan. To ensure coding reliability, coding discrepancies will be resolved through discussion and comparison of raw data. Coding will continue until a high reliability (Kappa= >0.80) is established. Once these data analyses are completed, the multidisciplinary team will provide the expert review of data, to discuss the interpretation of our findings in the context of current research on chronic heterogeneous pain. The same method was used successfully in our R34 grant.

Aim 2. To test in a small RCT pilot (N = 60 participants, 6 groups, 30/arm) the refined Active Brains with Fitbit versus Active Brains using the final adapted treatment manuals in preparation for a large RCT. We will report comparatively feasibility, credibility, acceptability and adherence between the 2 treatments. Feasibility will be assessed as depicted in the prior section. We will calculate the proportion of patients who complete at least 6 of the 8-planned treatment sessions (75%), along with the 95% confidence interval (CI) around this discontinuation rate. Treatments are considered feasible if over 70% of participants complete at least 6 treatment sessions. Adherence to treatment manual: We will assess adherence to treatment by listening to the audio recorded sessions, completing and analyzing the therapist adherence checklists. We will also rate adherence of study clinician in phase 2. The therapists will also

complete session adherence checklists. Adherence to Accelerometer and Fitbit DMD: We will report number of days participants in both groups wore the Accelerometers at baseline and at post test, and average number of days the FitBit was used in the p3RP-DMD group. The main purpose of our RCT is to compare feasibility, acceptability, credibility and adherence of the Active Brains with Fitbit and Active Brains. The trial is neither powered for efficacy nor aimed to provide such information. Justification for the sample of 30/group is depicted in the power consideration section. Consistent with the feasibility design of this trial, we will report means and SDs of all measures at all time points, including distribution of scores and internal consistency reliability. To determine the measures' sensitivity to detect change, we will report percent change in all quantitative outcomes within each group. Outcomes are: physical function/activity (self reported physical function and physical activity scales total scores, distance walked during the 6 minute walk test, and average number of steps and active minutes), emotional function (depression and anxiety), coping (catastrophizing, fear avoidance and coping style) and pain intensity. We will also describe types of activity (e.g., light, moderate and vigorous) and sedentary time as measured by the Accelerometers at pre and post in both groups. Within the Active Brains with Fitbit group, we will explore patterns of increased numbers of steps and active minutes daily, patterns of activity versus sedentary time, and number of blocks achieved. We will also summarize demographic and clinical variables. We will not conduct any efficacy analyses consistent with the R34 mechanism and prior research recommendations^{24,25} .

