Aim 2: We will conduct 2 nonrandomized open pilots (30 patients total, 15/arm) of the refined *Active Brains-Fitbit* versus the refined Active Brain for patients with chronic pain and MCI or MRP. We will collect quantitative survey and exit interview data about feasibility, acceptability, and credibility. We will also compare the credibility, feasibility, usability and adherence between the 2 treatments as well as all study procedures in preparation for an efficacy trial.

Specific aims for phase III are:

Aim 3: We will conduct a virtual randomized controlled trial of the Active Brains-Fitbit program versus an education control (Health Enhancement Program) in chronic pain patients with MCI or MRP (N = 40 total; 5-8/group). We will collect quantitative survey and exit interview data about feasibility, acceptability, and credibility. We will use data to further refine the programs. We will compare the credibility, feasibility, usability and adherence between the two programs, *Active Brains-Fitbit* and the HEP, as well as all study procedures in preparation for an efficacy trial.

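### The SAP plans and powers a 60-person RCT of Active Brains with Fitbit versus Active Brains, but the protocol's only RCT is Active Brains-Fitbit versus HEP with N = 40

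*SAP*

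**What the plan says.** **SAP.** The Analyses plan, Aim 2, sets out "To test in a small RCT pilot (N = 60 participants, 6 groups, 30/arm) the refined Active Brains with Fitbit versus Active Brains". It then states the purpose: "The main purpose of our RCT is to compare feasibility, acceptability, credibility and adherence of the Active Brains with Fitbit and Active Brains". The Power analyses paragraph, which is tied to Aim 2, says "With a sample size of N=60 participants the study will have 80% power to confirm feasibility of each delivery modality" if the true completion rate is at least 77%. Aim 2 refers back to that paragraph: "Justification for the sample of 30/group is depicted in the power consideration section". The decision rule is "Treatments are considered feasible if over 70% of participants complete at least 6 treatment sessions". The SAP has no Aim 3 and names HEP only in connection with a subsequent efficacy trial. It is dated June 1, 2018.

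**Protocol.** Under II. Specific Aims, the Fitbit and non-Fitbit versions are compared in Phase II: "We will conduct 2 nonrandomized open pilots (30 patients total, 15/arm"). Study Procedures, Phase II, lets participants choose a program until one group is full. Phase III is a "virtual randomized controlled trial of the Active Brains-Fitbit program versus an education control (Health Enhancement Program"), N = 40, in groups of 5–8, and the aim adds: "We will compare the credibility, feasibility, usability and adherence between the two programs". Study Procedures, Phase III, randomises in blocks of 12 and describes HEP as 8 sessions. Section V, Biostatistic Analysis, Phase II/Phase III, covers Fitbit data handling and qualitative coding only.

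**The concern.** The two documents disagree on which comparison is randomised, against what comparator, and with how many people. Feasibility is the trial's stated primary purpose, and the over-70% completion rule with its power statement is the only quantitative decision criterion. Both are attached to a trial that the protocol does not run.

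Two things could go wrong in reporting. The Fitbit versus non-Fitbit comparison, which is partly self-selected with 15 per arm, could be presented as randomised because the SAP says so. The actual RCT against HEP would also be reported without an analysis written for it. The SAP does not say that the completion rule covers HEP, and the promised comparison of usability appears nowhere in the SAP.

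**Working it through.** **1. The designs side by side**

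| | SAP Aim 2 | Protocol Phase II | Protocol Phase III |
|---|---|---|---|
| Comparison | Active Brains with Fitbit vs Active Brains | Same pair | Active Brains-Fitbit vs HEP |
| Randomised | Yes | No | Yes |
| N | 60 | 30 | 40 |
| Per arm | 30 | 15 | Not stated; 20 if split equally |
| Group size | 60/6 = 10 | Not stated | 5–8 |

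No protocol phase matches the SAP column. The figure of 60 under II. Specific Aims, Phase I, counts focus-group members (30 patients and 30 caregivers), so it does not supply the SAP's N.

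**2. Reproducing the SAP's 80%**

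Inputs from the SAP: threshold 70%, true completion rate 77%, 30 per arm. The SAP gives no test, alpha or method. The reading that fits is the chance that one arm's observed completion exceeds 70%:

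- Normal, variance at 0.70: Φ(0.07/√(0.70×0.30/30)) = 79.9%
- Normal, variance at 0.77: Φ(0.07/√(0.77×0.23/30)) = 81.9%
- Exact binomial, strict rule (at least 22 of 30): 76.2%

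The stated figure therefore holds by normal approximation at 30 per arm. Other readings do not fit. Pooling all 60 gives 90.1% (normal, variance at 0.77), and a one-sided 5% test of a 70% null at 30 per arm has only about 15–19% power.

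**3. The same calculation for the protocol's RCT**

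Twenty per arm is an assumption. The protocol intends equal numbers, but 40 = 3×12 + 4. On a single unstratified 1:1 list, three full blocks give 18 per arm and the last four participants can fall anywhere from 0 to 4 in one arm. Each arm can therefore hold 18 to 22.

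| n per arm | Normal (variance at 0.70 – at 0.77) | Exact, over 70% |
|---|---|---|
| 18 | 74.2–76.0% | 78.3% (≥13) |
| 19 | not needed for the range | 74.1% (≥14) |
| 20 | 75.3–77.2% | 69.6% (≥15) |
| 21 | not needed for the range | 81.0% (≥15) |
| 22 | 76.3–78.2% | 77.4% (≥16) |

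To keep 80% at 20 per arm, the true completion rate would have to be 77.8% (variance at the true rate), 78.6% (variance at 0.70) or 79.9% (exact), not 77%.

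**4. Precision of the completion rate**

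Wald 95% half-width at 77%:

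- n = 30: 1.96×√(0.77×0.23/30) = 15.1 points
- n = 20: 1.96×√(0.77×0.23/20) = 18.4 points

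**5. What carries over to HEP**

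Most SAP outputs do not depend on which arms are compared: completion of 6 of 8 sessions with its CI, the over-70% rule, accelerometer days, means and SDs, and percent change. HEP also has 8 sessions, so these can be applied unchanged. The comparator, N, power statement and 30-per-group justification cannot be carried over, and there is no usability analysis to carry over.

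**6. Likely origin, and a related slip**

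The SAP is dated 2018, and the protocol's reference 101 is a 2020 validation study of a mobile 6-minute walk test. The SAP appears not to have been updated when Phase III was written. Separately, the SAP's design paragraph confines Fitbit assessment to those randomised to Active Brains. Protocol section 3.1 and the SAP's own paragraph on device adherence place it in the Fitbit arm.

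**The case against.** The strongest reply is that the gap is narrow and its consequences small. SAP Aim 1 already covers focus groups, exit interviews, session completion, credibility and homework adherence, so it can be read as protocol Phases I and II. SAP Aim 2 would then be the RCT, needing only a new comparator, N and power sentence. Most outputs carry over, and the completion rule is written for treatments in general. The power loss is under 5 points by normal approximation. The exact 69.6% at 20 per arm is largely discreteness: 18, 21 and 22 per arm all give more than the exact 76.2% at 30, and an at-least-70% rule at 20 per arm would give 84.4%. The SAP also disclaims any efficacy analysis.

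Much of this stands. The power figures are illustrative, the exact values do not show a steady loss, and the widening of the interval is the clearer effect. It is also fair that usability is undefined in the protocol as well as absent from the SAP.

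None of it removes the mismatch. Even on the kindest mapping, the SAP's randomised comparison has the wrong comparator and the wrong N. The age of the SAP explains this but does not correct it, and no later analysis plan is provided.

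**Conclusion.** The concern holds and must be fixed. The SAP's comparator, randomised phase, sample size and stated power do not describe the RCT in the protocol. N is 40 rather than 60, one third fewer.

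Under the SAP's own inputs, and assuming 20 per arm, the chance of meeting the completion rule falls from 79.9–81.9% to 75.3–77.2% by normal approximation (76.2% to 69.6% exact). Over 18 to 22 per arm the range is 74.2–78.2% normal and 69.6–81.0% exact. These figures rest on an inferred method, since the SAP names none. The conclusion does not depend on them, because the mismatch is plain from the text.

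No hypothesis test or efficacy claim is affected. What is lost is pre-specification of the feasibility comparison with HEP and a correct statement of its precision.

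**What to change.** 1. **Restate SAP Aim 2 by phase.** Phase II: nonrandomised open pilots, 15 per program, with the planned between-program comparison kept but descriptive and labelled nonrandomised. The descriptive items now under SAP Aim 1 can be assigned here. Phase III: RCT of Active Brains-Fitbit versus HEP, N = 40, reporting session completion with its 95% CI, credibility, acceptability and adherence for both arms. Say explicitly that the over-70% rule applies to each arm, which follows the SAP's existing reference to each delivery modality. Define how usability is measured and reported, or remove it from the protocol's list.
2. **Replace the sample-size text.** Substitute a statement for N = 40 for both the N = 60 power sentence and the 30-per-group justification. Name the method (normal or exact, strict or non-strict threshold), label 20 per arm as an assumption, and give the expected CI half-width.
3. **Reconcile the Fitbit sentence** in the SAP's design paragraph with protocol section 3.1 and the SAP's device-adherence paragraph.
4. **Optionally,** state in both documents that no randomised contrast in this project isolates the Fitbit, so whether it is needed is left to the later trial.

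Items 1–3 are SAP rewording, plus a small protocol edit if usability is dropped; item 4 also touches protocol section 3.1. No new patients or visits are needed, unless a usability measure has to be specified. The price is a somewhat lower stated power by normal approximation and a Phase II comparison that is openly descriptive.

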Once questionnaires, MoCA, and the 6MWT have been completed, participants will be assigned to one of the two groups using a randomized block design (in blocks of 12 via [sealedenvelope.com](http://sealedenvelope.com)), to ensure that equal numbers of patients are split into the *Active Brains-Fitbit* or the HEP groups. Participants will be notified via email which group they have been assigned to. They will be told that they can participate in one of 2 programs, Active Brains 1 (which is the active intervention) or Active Brains 2 (which is the control group). If participants are assigned to the *Active Brains-Fitbit* group, a study staff will mail a Fitbit device with instructions to the participants. Participants will not be expected to pay for the device or any shipping costs.

One week prior to the start of the group, a research assistant will email all participants to begin wearing the accelerometer device. The research assistant will check-in with all participants via Zoom or phone the same day in order to ensure that there are no technological problems, as well as confirm that all participants are wearing the device properly. The study staff will continue to check in with participants throughout the one-week wear period to ensure adherence. After the one-week period, participants will be asked to return the ActiGraph device using the pre-paid shipping label and packaging provided. Participants will be asked to confirm that they have returned the device via mail. Following the one-week ActiGraph period,

all participants in the *Active Brains-Fitbit* group will pair their FitBit DMD to a smartphone with Bluetooth. A research assistant will schedule a time with all participants to provide guidance via Zoom on how to sync their Fitbit device to their personal phone. Participants in the *Active Brains-Fitbit* group will begin wearing their device for the duration of the program once the device is synced to the participant's phone.

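### The SAP's 80% power to confirm feasibility is only the approximate chance that observed completion exceeds 70%; no error rate is stated, and a passing result need not show that true completion is above 70%

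*SAP*

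**What the plan says.** The SAP's Power analyses paragraph first sets the purpose of the trial: "This trial (Aim 2) is primarily focused on feasibility and acceptability, not statistical significance of efficacy". It then states that, with 60 participants, "the study will have 80% power to confirm feasibility of each delivery modality". The condition attached to this is a true rate of 77% or more. The paragraph names no alpha, sidedness or completion rate that would count as unacceptable.

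The decision rule is under Analyses plan, Aim 2, for a "small RCT pilot (N = 60 participants, 6 groups, 30/arm": "Treatments are considered feasible if over 70% of participants complete at least 6 treatment sessions". The same paragraph plans to report the proportion completing at least 6 of the 8 sessions, "along with the 95% confidence interval (CI) around this discontinuation rate". The rule does not refer to that interval.

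The protocol's Phase III trial has a different comparator (the Health Enhancement Program) and a different size, "N = 40 total; 5-8/group" (II. Specific Aims, Aim 3). Its Phase III procedures describe blocked randomisation "to ensure that equal numbers of patients are split into the" two arms. The protocol gives no completion threshold and no power statement.

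**The concern.** Power to confirm suggests a test: a rate to be ruled out, a limited chance of ruling it out wrongly, and an 80% chance of succeeding when the truth is good. The SAP supplies only the last of these. What it calls confirmation is an observed proportion above 70%, which sampling variation alone can produce in an arm whose true completion is below that level.

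This is the only numerical feasibility threshold in either document, and the SAP refers to the power section to justify 30 per group. A reader told that feasibility was confirmed with 80% power would assume a controlled error rate and give the result more weight than 30 participants per arm can bear.

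**Working it through.** **Inputs.** From the SAP: 30 per arm, assumed true completion 77%, claimed power 80%, and a pass when observed completion is strictly above 70%. Since 21/30 is exactly 70.0%, the smallest pass is 22/30 = 73.3%. My assumption: participants are independent.

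**1. Reproducing the 80%.** Under the written rule, the quantity is the chance that observed completion exceeds 70% when the truth is 77%.
- Normal approximation: Φ[(0.77 − 0.70)/√(0.77 × 0.23/30)] = Φ(0.07/0.0768) = Φ(0.911) = 81.9%.
- Exact binomial: P(X ≥ 22 | n = 30, p = 0.77) = 76.2%.
- A true rate of about 77.9% is needed for the exact probability to reach 80%.

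So the 80% is roughly the probability of passing the written rule. It is about 4 points too high when calculated exactly.

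**2. Chance of passing when true completion is at or below 70%**, P(X ≥ 22 | n = 30, p):

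| True completion | Chance of passing |
|---|---|
| 50% | 1% |
| 55% | 3% |
| 60% | 9.4% |
| 65% | 22.5% |
| 70% | 43.2% |

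**3. What the smallest pass shows.** The exact (Clopper-Pearson) two-sided 95% interval for 22/30 is 54.1% to 87.7%. It includes rates well below 70%.

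**4. What a bound above 70% would require.** The one-sided 95% exact lower bound is 68.1% for 25/30 and 72.0% for 26/30, so 26/30 is needed. The chance of reaching 26/30 when the truth is 70% is 3.0%. At higher true rates:

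| True completion | P(X ≥ 26), n = 30 |
|---|---|
| 77% | 15% |
| 85% | 52% |
| 90% | 82% |
| 95% | 98% |

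Using the lower limit of the two-sided 95% interval instead, 26/30 falls just short (69.3%) and 27/30 is needed (73.5%).

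**5. If the rule were carried to the protocol's N = 40.** Neither document says that it is. An equal split gives about 20 per arm. Since 14/20 is exactly 70%, passing needs 15/20 (exact 95% interval 51% to 91%). The chance of passing is 70% at a true 77%, and 13%, 25% and 42% at true rates of 60%, 65% and 70%.

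**The case against.** The strongest reply is that this is a feasibility pilot. Point-estimate criteria are ordinary in pilots, and the SAP defines what it means by feasible. Under that definition the 80% is approximately right, and a program well below the bar is usually rejected (9% pass at a true 60%, 3% at 55%). All of this stands, and it is why the criterion itself can stay. It does not rescue the wording. The SAP disclaims inference about efficacy, not about feasibility, and on feasibility it makes an explicit power claim.

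Some stronger readings are tempting but not supported:

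- *The 43% at a true 70% shows a defective rule.* Almost any point-estimate rule passes roughly half the time when the truth sits on the threshold. The rates at 60% and 65% are more informative.
- *No error rate lies behind the 80%.* The documents support only that none is stated. For example, an exact test of all 60 participants against 60%, passing at 44/60, has alpha 2.2% and power 79.9% at 77%. That origin is speculative: 60% appears nowhere as an unacceptable rate, the test pools the arms although the SAP speaks of each modality, and it is not the 70% rule.
- *The real power is 15%, not 80%.* The 15% belongs to a stricter meaning of confirm that the SAP does not adopt.
- *The threshold decides whether a program goes to a large trial.* The SAP describes groundwork and preparation for that trial and attaches no go/no-go rule to this figure.
- *The interval is attached to the wrong quantity.* Completion and discontinuation are complements, so an interval for one gives the interval for the other. This is a wording slip.

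**Conclusion.** The point holds as a matter of what the SAP claims for its rule. The stated 80% is an approximate probability of observing more than 70% completion in an arm at a true 77%. Calculated exactly for 30 per arm it is 76%. The same rule passes an arm truly at 60%, 65% or 70% in 9%, 22% or 43% of trials, and its smallest passing result is compatible with completion as low as 54%. Passing therefore does not by itself confirm completion above 70%, and the SAP states no error rate that would support that word.

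The 30-per-arm figures rest on the SAP's own design and on independent participants. Treatment is delivered in groups. Positive correlation within groups would widen the intervals, but the documents give no value for it. The 20-per-arm figures rest on the further assumption that the SAP rule applies to the protocol's Phase III trial, so they are illustrative only.

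**What to change.** 1. **SAP, Power analyses.** Replace the claim of 80% power to confirm feasibility with: *about 76% probability (exact binomial) that observed completion exceeds 70% in an arm of 30 if the true rate is 77%*. Print beside it the pass probabilities at true rates of 60%, 65% and 70% (9%, 22%, 43%). If the rule is meant for the protocol's N = 40, say so and give the 20-per-arm figures instead.
2. **SAP, Analyses plan, Aim 2.** Keep observed completion above 70% as a descriptive feasibility criterion. Report it with the exact 95% interval for the completion rate, correcting the reference to discontinuation.
3. **Same place.** Use the word confirmed only if the lower confidence bound for completion exceeds 70%, and state which bound is meant. With a one-sided 95% exact bound this needs 26/30.

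A formal multi-category rule is not required. One that demanded a bound to pass but only a point estimate to fail would be lopsided.

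The cost is wording; no extra participants are needed. The downside is a less favourable stated figure and conclusion: at the SAP's assumed 77%, the stricter word would be earned only 15% of the time. It would be earned 82% of the time at a true 90% and 98% at 95%. The SAP cites 100% retention in earlier studies of the parent program in a different population. If completion here came close to that, the stricter wording would usually be available.

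### Sensitivity to change rests on within-group percent change alone, with its form undefined and no SD of change or pre-post correlation planned

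*SAP*

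**What the plan says.** The SAP's Analyses plan for Aim 2 sets out to determine how sensitive the measures are to change and gives one statistic for it: "sensitivity to detect change, we will report percent change in all quantitative outcomes within each group". No formula follows. The outcome list that comes next has 11 entries: self-reported physical function, self-reported physical activity, "distance walked during the 6 minute walk test, and average number of steps and active minutes", depression, anxiety, catastrophizing, fear avoidance, coping style and pain intensity.

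Other planned quantitative output:

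- The preceding sentence in Aim 2 says "we will report means and SDs of all measures at all time points, including distribution of scores and internal consistency reliability".
- Aim 1 says "We will also calculate descriptive statistics for quantitative measures", without naming them.
- Protocol section V (Biostatistic analysis) deals with qualitative coding and the handling of Fitbit data. It contains no analysis of quantitative change.

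On scope, the SAP states "The trial is neither powered for efficacy nor aimed to provide such information" and "We will not conduct any efficacy analyses". It also describes the pilot as "using the final adapted treatment manuals in preparation for a large RCT", and its opening section lists the measurements among the things the project will refine.

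**The concern.** Sensitivity to change is a matter of signal against noise, and percent change carries only the signal. The same percentage can come from a change nearly everyone shares or from one buried in scatter.

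The form is also open. Change in the group mean divided by the baseline mean, and the average of each participant's own percentage, are different quantities. The second can be above zero when nothing has changed on average, because participants with low baseline values produce large positive percentages.

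A percentage also depends on where a scale's zero lies, so walk distance, step counts and questionnaire scores do not share a common footing.

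What is at stake is modest. The SAP wants to refine its measures ahead of a larger trial, and the one figure named for the purpose does not tell a consistent measure from a noisy one. Two quantities that paired data supply directly, the SD of change and the pre-post correlation, are absent from the planned output.

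**Working it through.** The plan states no figure that depends on this sentence, so there is nothing to reproduce. The documents supply two inputs: 30 per arm (SAP, Aim 2) and a 77% completion rate (SAP, Power analyses). Using 77% as the share with both assessments is an assumption. All means, SDs, correlations and coefficients of variation (CV) below are also assumptions.

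**1. What the planned output yields.** Means and SDs at each time point give mean change divided by baseline SD, provided the same participants enter both means. The SD of change needs the pre-post correlation r:

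SD of change = √(SD₁² + SD₂² − 2·r·SD₁·SD₂), and standardised response mean (SRM) = mean change / SD of change.

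Take a mean going from 50 to 55 with SD 10 at both times. This is +10%, or 0.5 baseline SD. With equal SDs, SD of change = 10·√(2(1 − r)).

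| r | SD of change | SRM |
|---|---|---|
| 0 | 14.1 | 0.35 |
| 0.3 | 11.8 | 0.42 |
| 0.5 | 10.0 | 0.50 |
| 0.7 | 7.7 | 0.65 |
| 0.9 | 4.5 | 1.12 |

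Percent change, both means and both SDs are the same in every row, so the planned summaries cannot tell the rows apart.

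**2. Percent change alone.** Keep 50 to 55 and r = 0.5, so that SD of change equals SD. With SD 5, 10 or 20, the SRM is 5/5 = 1.00, 5/10 = 0.50 or 5/20 = 0.25. Percent change is 10% each time.

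**3. The two forms.** Suppose the pre and post distributions are identical and lognormal, with raw-scale correlation r. Change in the group mean is 0%. The mean individual percent change is (1 + CV²)/(1 + r·CV²) − 1. For example, CV 0.5 and r 0.5 give 1.25/1.125 − 1 = 11.1%, and a simulation agreed.

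| CV | r = 0.3 | r = 0.5 | r = 0.7 |
|---|---|---|---|
| 0.3 | 6.1% | 4.3% | 2.5% |
| 0.5 | 16.3% | 11.1% | 6.4% |
| 0.7 | 29.9% | 19.7% | 11.0% |

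**4. Precision of the proposed replacement.** For an SRM of 0.5, SE = √(1/n + 0.5²/(2n)).

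- n = 30: SE 0.194, 95% CI 0.12 to 0.88.
- n = 23 (0.77 × 30 = 23.1): SE 0.221, 95% CI 0.07 to 0.93.

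Exact noncentral-t intervals are 0.12 to 0.88 and 0.06 to 0.93.

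**5. Planning use.** Assume a later two-arm comparison at d = 0.5, 80% power and two-sided 5%, ignoring group clustering and any third arm. Then n per arm = 2·((1.960 + 0.842)/0.5)² = 62.8, so 63. Baseline adjustment multiplies 62.8 by (1 − r²):

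- r = 0.3: 57.1, so 58.
- r = 0.5: 47.1, so 48.
- r = 0.7: 32.0 (just above 32), so 33.

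A pilot correlation of 0.5 from 30 pairs has a Fisher-z 95% CI of 0.17 to 0.73, so it is a rough guide only.

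**The case against.** The strongest reply is about weight. No sample size, decision rule or test rests on this sentence. Efficacy analyses are ruled out, so no error rate depends on prespecification, and the missing figures could be computed later from the participant-level data. The preceding sentence already promises SDs, so variability is not ignored and a baseline-SD effect size is within reach. All of this stands, and it is why the point is minor. It does not supply the SD of change or the correlation, and it does not settle the form of percent change before results are seen.

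Other parts of the reply stand to a degree:

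- **Form.** After a promise of group means, change in the group mean is the more natural reading. The artefact in step 3 needs the other reading plus lognormal data. The text still permits both.
- **Cross-scale comparison.** The SAP does not propose to rank outcomes by percent change. The caution concerns how a reader may use the figures.
- **Planning.** The SAP does not say that the pilot will supply variances for the later trial. Step 5 shows an added benefit and does not test a stated aim.
- **The SRM shares a weakness.** A low value may mean an insensitive measure or participants who did not change. The same is true of percent change, which also omits the noise.
- **Sample size.** The 30 per arm is the SAP's figure. Protocol section II (Specific aims) describes 15 per arm, nonrandomised, in Phase II and N = 40 in the randomised Phase III. By the same formulae, 20 pairs give an SRM interval of about 0.04 to 0.96 and a correlation interval of 0.07 to 0.77. Fifteen pairs give about −0.04 to 1.04 and −0.02 to 0.81. Smaller arms weaken the planning value but not the case for showing the uncertainty.

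**Conclusion.** The concern holds. The SAP gives itself the task of describing sensitivity to change and names a statistic with no variability term and no stated form. None of the other planned output yields the SD of change or the pre-post correlation.

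The consequence is limited to a secondary descriptive aim, and the feasibility conclusion does not depend on it. The sizes are illustrations on assumed inputs. An identical set of planned summaries is compatible with an SRM of 0.42 to 0.65 over correlations of 0.3 to 0.7. With no change on average, the two forms of percent change differ by about 3 to 30 percentage points over CVs of 0.3 to 0.7. The claim itself rests on the text and does not depend on these values.

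**What to change.** Replace the sentence in SAP Aim 2 with:

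> To describe the measures' sensitivity to change, for each outcome and arm, among participants with both assessments, we will report n, mean change, SD of change, pre-post correlation, and the standardised response mean (mean change divided by SD of change) with 95% CI. Percent change will be a supplementary figure, defined as change in the group mean divided by the baseline group mean in the same participants, and will not be compared across scales. These are within-arm descriptive figures, with no between-arm test, no p-values, no efficacy reading and no firm ranking of outcomes. A low value may reflect an insensitive measure or participants who did not change.

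The cost is this text and a little programming. No new data are needed for the SAP's outcomes: the SAP plans summaries of all measures at all time points, and the protocol's Phase III procedures repeat the questionnaires, accelerometer and walk test at post-test. There are two downsides. The intervals will be wide, and wider with dropout or smaller arms. A within-arm interval that excludes zero could also be misread as efficacy, which is why the descriptive label belongs in the text.
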